Appendix 1.6: Subjects Receiving Investigational Medicinal Product from Specific Batches

Listing 1-6: Subjects Receiving Investigational Medicinal Product from Specific Batches

Appendix 1.7: Randomisation Scheme and Codes

Listing 1-7: Randomisation

Patient Data Listings (Appendix 2)

Appendix 2.1: Discontinued Subjects

Listing 1-1 Screening failures

Listing 1-2 Reason(s) for withdrawal from the trial

Appendix 2.2: Protocol Deviations

Listing 2-1 Protocol deviations

Listing 2-2 Comments from CRF

Appendix 2.3: Trial Analysis Sets

Listing 3-1 Trial analysis sets

Listing 3-2 Reasons for exclusion from analysis sets

Appendix 2.4: Demographic Data

Listing 4-1 Demographics

Listing 4-2 Date of first AK diagnosis

Listing 4-3 AK treatment history

Listing 4-4 History of SCC

Listing 4-5 Actual trial period

Listing 4-6 Medical history

Listing 4-7 Concomitant diagnoses at baseline

Listing 4-8 Concomitant medication

Listing 4-9 Concomitant treatment and procedures

Trial ID: LP0041-63	Date: 28-AUG-2019	Version: Final 1.0 Page 23 of 32
---------------------	--------------------------	-------------------------------------

Listing 4-10 Vital signs

Appendix 2.5: Compliance and/or Investigational Product Concentration Data

Listing 5-1 Compliance

Listing 5-2 Drug accountability

Appendix 2.6: Efficacy Data

Listing 6-1 AK lesion count

Appendix 2.7: Safety Data

Listing 7-1 Deaths

Listing 7-2 Serious adverse events

Listing 7-3 Subjects withdrawn from trial due to adverse events

Listing 7-4 Subjects withdrawn from trial due to LSRs

Listing 7-5 Severe adverse events

Listing 7-6 Adverse events

Listing 7-7 Suspicion of neoplasia and biopsy results

Appendix 2.8: Listing of Laboratory Values by Subject

Listing 8-1 Physical Examination

Listing 8-2 Laboratory measurements – urinalyses

Listing 8-3 Vital Signs

Additional Tables for Results Reporting in Clinical Trial Data Registries

Table 4-1 Age group: all randomised subjects

Table 4-2 Age and sex: safety analysis set

Table 4-3 Age and sex: full analysis set

Table 4-4 Age and sex: PP analysis set

Table 4-5 Non-serious AEs occurring in $\geq 5\%$ subjects by MedDRA primary SOC and PT: safety analysis set

Appendix II

Table shells

Shell 1: Subject disposition: safety analysis set

	Ingenol mebutate (n=xxx)		Imiquimod (n=xxx)		Total (n=xxx)	
	N ¹	(%)	N	(%)	N	(%)
Randomised (FAS ²)	xxx	(xx.x)	xxx	(xx.x)	xxx	(xx.x)
Safety analysis set	xxx	(xx.x)	xxx	(xx.x)	xxx	(xx.x)
Withdrawals	xxx	(xx.x)	xxx	(xx.x)	xxx	(xx.x)
Completers	xxx	(xx.x)	xxx	(xx.x)	xxx	(xx.x)
PP analysis set	xxx	(xx.x)	xxx	(xx.x)	xxx	(xx.x)
Total	xxx	(xxx.x)	xxx	(xxx.x)	xxx	(xxx.x)

- 1) N: Number of subjects
- 2) FAS: Full analysis set

Shell 2: History of SCC: safety analysis set

History of SCC ¹	Ingenol mebutate (n=xxx)		Imiquimod (n=xxx)	
	N ²	(%)	N	(%)
Yes	xxx	(xx.x)	xxx	(xx.x)
Present diagnosis	xxx	(xx.x)	xxx	(xx.x)
Less than 12 month ago	xxx	(xx.x)	xxx	(xx.x)
More than 12 month ago	xxx	(xx.x)	xxx	(xx.x)
No	xxx	(xx.x)	xxx	(xx.x)
Total	xxx	(xxx.x)	xxx	(xxx.x)

- 1) SCC: Squamous cell carcinoma
- 2) N: Number of subjects

Shell 3: Exposure – number of treatment cycles by [country/anatomical location/history of SCC]: safety analysis set

Number of treatment cycles by [country/anatomical location/history of SCC]	Ingenol mebutate (n=xxx)		Imiquimod (n=xxx)	
	N ¹	(%)	N ¹	(%)
<Subgroup 1>				
1	xxx	(xx.x)	xxx	(xx.x)
2	xxx	(xx.x)	xxx	(xx.x)
<Subgroup 2>				
⋮				
Total				
1	xxx	(xx.x)	xxx	(xx.x)
2	xxx	(xx.x)	xxx	(xx.x)

1) N: Number of subjects

Shell 4: Histological diagnoses of biopsies: safety analysis set

Histological diagnosis	Ingenol mebutate (n=xxx)		Imiquimod (n=xxx)	
	N ¹	(%)	N ¹	(%)
Actinic Keratosis	xxx	(xx.x)	xxx	(xx.x)
In Situ SCC/Bowen	xxx	(xx.x)	xxx	(xx.x)
Invasive SCC	xxx	(xx.x)	xxx	(xx.x)
BCC	xxx	(xx.x)	xxx	(xx.x)
Other Neoplasia	xxx	(xx.x)	xxx	(xx.x)
No malignant findings	xxx	(xx.x)	xxx	(xx.x)
Total	xxx	(xxx.x)	xxx	(xxx.x)

1) N: Number of subjects

Shell 5: Incidence of SCC [and other neoplasia] in the treatment area from [baseline/Week 20] to end of trial: [safety/per protocol] analysis set

SCC ¹ [and other neoplasia ²]	Ingenol mebutate (n=xxx) N ³ (%) E ⁴	Imiquimod (n=xxx) N ³ (%) E ⁴
[SCC/SCC and other neoplasia ⁵]	xxx (xx.x) xx	xxx (xx.x) xx
No SCC [or other neoplasia]	xxx (xx.x) xx	xxx (xx.x) xx
Cumulative incidence (%)	xx.x	xx.x
Lower 95% CI ⁶ (%)	xx.x	xx.x
Upper 95% CI (%)	xx.x	xx.x

- 1) SCC: Squamous Cell Carcinoma
- 2) SCC and other neoplasia include SCC, BCC, and in situ BCC/Bowens
- 3) N: Number of subjects
- 4) E: Number of events
- 5) XXX subject in xxx treatment group had two incidences of SCC [and other neoplasia]
- 6) CI: Confidence interval

NOTE: If any incidence of other neoplasia exists with details specified in a text field describing the type, then this must be discussed with the medical expert to identify malignant diagnoses

Shell 6: Annual incidence of SCC [and other neoplasia] in the treatment area from baseline to Month 12, 24, and 36: [safety/per protocol] analysis set

SCC ¹ [and other neoplasia ²]	Ingenol mebutate (n=xxx)	Imiquimod (n=xxx)
Subject years at Month 12	xxx.x	xxx.x
Month 12 cumulative incidence rate (%)	xx.x	xx.x
Lower 95% CI (%)	xx.x	xx.x
Upper 95% CI (%)	xx.x	xx.x
Subject years at Month 24	xxx.x	xxx.x
Month 24 cumulative incidence rate (%)	xx.x	xx.x
Lower 95% CI (%)	xx.x	xx.x
Upper 95% CI (%)	xx.x	xx.x
Subject years at Month 36	xxx.x	xxx.x
Month 36 cumulative incidence rate (%)	xx.x	xx.x
Lower 95% CI (%)	xx.x	xx.x
Upper 95% CI (%)	xx.x	xx.x

- 1) SCC: Squamous Cell Carcinoma
- 2) SCC and other neoplasia include SCC, BCC, in situ BCC/Bowens
- 3) CI: Confidence Interval

NOTE: If any incidence of Other neoplasia exists with details specified in a text field describing the type, then this must be discussed with medical expert to identify malignant diagnoses

Shell 7: Summary of SCC [and other neoplasia] in the treatment area from baseline to end of trial: [safety/per protocol] analysis set

SCC ¹ [and other neoplasia ²]	Ingenol Mebutate (n=xxx)	Imiquimod (n=xxx)
Incidence rate ^[2/3]	xx.xx	xx.xx
Number of incidences		
0	x (xx.xx%)	x (xx.xx%)
1	x (xx.xx%)	x (xx.xx%)
2	x (xx.xx%)	x (xx.xx%)
.		
.		
Total	x (xx.xx%)	x (xx.xx%)
Diagnosis		
Invasive SCC	x (xx.xx%)	x (xx.xx%)
BCC	x (xx.xx%)	x (xx.xx%)
.		
.		
Missing	x (xx.xx%)	x (xx.xx%)
Total	x (xx.xx%)	x (xx.xx%)

1) SCC: Squamous Cell Carcinoma

2) SCC and other neoplasia include SCC, BCC, and in situ BCC/Bowens

3) Incidence rate: 100*(number of events/number of patient years)

NOTE: Diagnosis is only for the secondary endpoint

Shell 8: Incidence of SCC [and other neoplasia] by subgroups: [safety/per protocol] analysis set

Number of subjects with SCC ¹ [and other neoplasia ²] by subgroup	Ingenuol mebutate (n=xxx)				Imiquimod (n=xxx)			
	N ³	n ⁴	(% ⁵)	E ⁶	N ³	n ⁴	(% ⁵)	E ⁶
Anatomical location								
Face	xxx	x	(xx.x)	xx	xxx	x	(xx.x)	xx
Scalp	xxx	x	(xx.x)	xx	xxx	x	(xx.x)	xx
Country								
France	xxx	x	(xx.x)	xx	xxx	x	(xx.x)	xx
Germany	xxx	x	(xx.x)	xx	xxx	x	(xx.x)	xx
United Kingdom	xxx	x	(xx.x)	xx	xxx	x	(xx.x)	xx
Sex								
Male	xxx	x	(xx.x)	xx	xxx	x	(xx.x)	xx
Female	xxx	x	(xx.x)	xx	xxx	x	(xx.x)	xx
Fitzpatrick skin type								
I	xxx	x	(xx.x)	xx	xxx	x	(xx.x)	xx
II	xxx	x	(xx.x)	xx	xxx	x	(xx.x)	xx
III	xxx	x	(xx.x)	xx	xxx	x	(xx.x)	xx
IV	xxx	x	(xx.x)	xx	xxx	x	(xx.x)	xx
History of SCC								
Yes	xxx	x	(xx.x)	xx	xxx	x	(xx.x)	xx
No	xxx	x	(xx.x)	xx	xxx	x	(xx.x)	xx

- 1) SCC: Squamous Cell Carcinoma
- 2) SCC and other neoplasia includes SCC, BCC, and in situ BCC/Bowens
- 3) N: Number of subjects in subgroup
- 4) n: Number of subjects with SCC [and other neoplasia] in subgroup
- 5) %: Percentage of subjects in the subgroup with SCC [and other neoplasia]
- 6) E: Number of events

NOTE: Subgroups might change

[figure not shown]
Shell 9: Difference in incidence of SCC [and other neoplasia] in the treatment area from baseline to Month 36: [safety/per protocol] analysis set

SCC ¹ [and other neoplasia ²]	Ingenol mebutate (n=xxx)	Imiquimod (n=xxx)
Incidence rate (%)	xx.x	xx.x
Lower 95% CI (%)	xx.x	xx.x
Upper 95% CI (%)	xx.x	xx.x
Difference		xx.x
Lower 95% CI (%)		xx.x
Upper 95% CI (%)		xx.x

- 1) SCC: Squamous Cell Carcinoma
- 2) SCC and other neoplasia include SCC, BCC, and in situ BCC/Bowens
- 3) XXX subject in xxx treatment group had two incidences of SCC [and other neoplasia]
- 4) CI: Confidence interval

Shell 10: Time to SCC: [safety/per protocol] analysis set

Shell 11: [Complete/Partial] clearance by visit: [full/ per protocol] analysis set

[Complete/Partial ¹] clearance	Ingenol mebutate (n=xxx)		Imiquimod (n=xxx)	
	N ²	(%)	N ²	(%)
Week 8				
Cleared	xxx	(xx.x)	xxx	(xx.x)
Not cleared	xxx	(xx.x)	xxx	(xx.x)
Total	xxx	(xxx.x)	xxx	(xxx.x)
Lower 95% CL ³ (Cleared)		(xx.x)		(xx.x)
Upper 95% CL ³ (Cleared)		(xx.x)		(xx.x)
Week 16⁴				
Cleared	xxx	(xx.x)	xxx	(xx.x)
Not cleared	xxx	(xx.x)	xxx	(xx.x)
Total	xxx	(xxx.x)	xxx	(xxx.x)
Lower 95% CL ³ (Cleared)		(xx.x)		(xx.x)
Upper 95% CL ³ (Cleared)		(xx.x)		(xx.x)
.				
.				
.				
Month 36				
Cleared	xxx	(xx.x)	xxx	(xx.x)
Not cleared	xxx	(xx.x)	xxx	(xx.x)
Total	xxx	(xxx.x)	xxx	(xxx.x)
Lower 95% CL ³ (Cleared)		(xx.x)		(xx.x)
Upper 95% CL ³ (Cleared)		(xx.x)		(xx.x)

- 1) Partial clearance: At least 75% reduction in AK count
- 2) N: Number of subjects
- 3) CL: Confidence limit
- 4) Only subjects with two treatment courses attend visit at Week 16

Shell 12: Analysis of [complete/partial] clearance [after the last treatment cycle/at month 12]: [full/ per protocol] analysis set

[Complete/Partial ¹] clearance	Ingenol mebutate (n=xxx)		Imiquimod (n=xxx)	
	N ²	(%)	N ²	(%)
[After last treatment cycle^{3,4}/Month 12]				
Cleared	xxx	(xx.x)	xxx	(xx.x)
Not cleared	xxx	(xx.x)	xxx	(xx.x)
Total	xxx	(xxx.x)	xxx	(xxx.x)
Lower 95% CL ⁵ (Cleared)		(xx.x)		(xx.x)
Upper 95% CL ⁵ (Cleared)		(xx.x)		(xx.x)
Ratio of clearance rates ⁶			xx.xx	
95% CI ⁷			xx.xx to xx.xx	
p-value			x.xxx	

- 1) Partial clearance: At least 75% reduction in AK count
- 2) N: Number of subjects
- 3) Last treatment cycle is at Week 8 or Week 16
- 4) Subjects who were not clear at week 8 and by mistake not entered second treatment cycle are excluded
- 5) CL: Confidence limit
- 6) Cochran-Mantel-Haenszel estimate stratified by country, anatomical location and history of SCC
- 7) CI: Confidence interval

Signature Page for TMF-000141169 v1.0

Reason for signing: Approved	Manager Verdict(s) Name: PPD Capacity: Date of signature: 28-Aug-2019 12:29:26 GMT+0000
------------------------------	---

Reason for signing: Approved	Manager(s) Name: PPD Capacity: Date of signature: 28-Aug-2019 13:47:29 GMT+0000
------------------------------	---

Reason for signing: Approved	QC App Name: PPD Capacity: Date of signature: 30-Aug-2019 07:57:28 GMT+0000
------------------------------	---

Electronic signatures made within eTMF LEO are considered to be a legally binding equivalent of traditional handwritten signatures.

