## 10.10.6 Safety Analysis

### 10.10.6.1 Analysis of Primary and Secondary Safety Endpoints

The primary endpoint and secondary safety endpoint are listed in sections [10.9.1](#) and [10.9.2](#) respectively. Both endpoints will follow the same method of analysis.

The 3-year cumulative incidence will be calculated for each treatment group using methods of survival analysis for estimation of cumulative incidence in the presence of censored time-to-event data. Annual incidence rates will also be presented for each group. The cumulative incidence rates will be presented for the event of SCC as primary endpoint and for SCC and other neoplasia as secondary. No formal statistical test comparing the two arms will be performed. For descriptive purposes, as an additional analysis, the difference in cumulative incidence rates between the two arms will be estimated and presented together with its 95% confidence interval.

A landmark analysis, conditional on patients' responses at Week 20, will additionally be performed in order to exclude SCC and other neoplasia reported within the first 20 weeks which are not assumed to be associated with the study treatment. Patients who experience a neoplasia before the 20-week landmark time point are excluded from the time-to-event analysis, which is otherwise conducted as above.

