7.5 General Principles

7.5.1 Statistical Analysis

In general, all output will be presented by treatment group where nothing else is mentioned. Descriptive statistics for all endpoints will be presented by treatment group and visit (if applicable) using observed cases, i.e. no imputation of missing data will be performed. Summaries by subgroup will include presentation of the endpoint in question by subgroup and overall.

Continuous data will be presented using the number of subjects, mean, standard deviation (SD), median, minimum, and maximum as described in the protocol. In addition, lower and upper quartile will be presented. Both the absolute values and the relative change from baseline will be presented.

Statistical tests will be performed as described in the protocol unless otherwise detailed.

Medical history and AEs are coded using MedDRA version 15.1.

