7.5.6 Changes to the Protocol

- The CCTP states: “*An interim analysis of trial data, obtained when approximately half of the trial period has elapsed, will be conducted. Assuming the time schedule shown in section 10.2, this will be prepared 3 years after study start. The interim analysis will not impact the conduct of this trial.*” This interim analysis was not conducted since the Pharmacovigilance Risk Assessment Committee at the European Medicines Agency found that the Periodic Safety Update Report was satisfactory.
- The CCTP states: “*A per protocol (PP) analysis set will be used as safety and efficacy subsets and will be defined as subjects in the FAS who complete the trial without major protocol deviations.*” Only deviations having impact on safety or efficacy will be considered. As the primary analysis is a time-to-event analysis, subjects will be censored from the PP analysis at the time of the deviation, i.e. the subject will be in the PP analysis set until the day when the deviation takes place.
- To support the primary endpoint, descriptive statistics of demographic and other baseline characteristics will be presented for the safety analysis set and not for the FAS as described in the CCTP.
- Reason for premature discontinuation from treatment is not presented as it is not captured in the eCRF. Reason for not applying trial medication according to protocol is listed.

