- Table 2-8 Annual incidence of SCC in the treatment area: per protocol analysis set [[Shell 6](#)]
- Table 2-9 Summary of SCC in the treatment area from baseline to end of trial: safety analysis set [[Shell 7](#)]
- Table 2-10 Summary of SCC in the treatment area from baseline to end of trial: per protocol analysis set [[Shell 7](#)]
- Table 2-11 Annual incidence of SCC and other neoplasia in the treatment area: safety analysis set [[Shell 6](#)]
- Table 2-12 Annual incidence of SCC and other neoplasia in the treatment area: per protocol analysis set [[Shell 6](#)]
- Table 2-13 Incidence of SCC in the treatment area by subgroups: safety analysis set [[Shell 8](#)]
- Table 2-14 Incidence of SCC in the treatment area by subgroups: per protocol analysis set [[Shell 8](#)]
- Table 2-15 Incidence of SCC and other neoplasia in the treatment area by subgroups: safety analysis set [[Shell 8](#)]
- Table 2-16 Incidence of SCC and other neoplasia in the treatment area by subgroups: per protocol analysis set [[Shell 8](#)]
- Table 2-17 Incidence of SCC and other neoplasia in the treatment area from week 20 to month 36: safety analysis set [[Shell 5](#)]

Trial ID: LP0041-63	Date: 28-AUG-2019	Version: Final 1.0 Page 19 of 32
---------------------	--------------------------	-------------------------------------

Table 2-18 Incidence of SCC and other neoplasia in the treatment area from week 20 to month 36: per protocol analysis set [[Shell 5](#)]

Table 2-19 Difference in the incidence of SCC in the treatment area: safety analysis set [[Shell 9](#)]

Table 2-20 Difference in the incidence of SCC in the treatment area: per protocol analysis set [[Shell 9](#)]

Table 2-21 Difference in the incidence of SCC and other neoplasia in the treatment area: safety analysis set [[Shell 9](#)]

Table 2-22 Difference in the incidence of SCC and other neoplasia in the treatment area: per protocol analysis set [[Shell 9](#)]

Adverse events

Table 2-23 Overall summary of adverse events from start of treatment to end of trial: safety analysis set

Table 2-24 Overall summary of adverse events from start of treatment to Week 20: safety analysis set

Table 2-25 Overall summary of adverse events from Week 20 to end of trial: safety analysis set

Table 2-26 Overall summary of adverse events by period: safety analysis set

Table 2-27 Adverse events from start of treatment to Week 20 by SOC: safety analysis set

Table 2-28 Adverse events by SOC: safety analysis set

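### The SCC subgroup tables give only a crude percentage that ignores censoring; adding subject-years and a rate would stop unequal follow-up from distorting subgroup comparisons

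*SAP*

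**What the plan says.** **Subgroup tables.** SAP Appendix I lists Table 2-13, "Incidence of SCC in the treatment area by subgroups: safety analysis set", and Table 2-14, "Incidence of SCC in the treatment area by subgroups: per protocol analysis set". Tables 2-15 and 2-16 do the same for SCC and other neoplasia. All four use Shell 8 in Appendix II. Its footnotes define the denominator as "N: Number of subjects in subgroup", the numerator as "n: Number of subjects with SCC [and other neoplasia] in subgroup" and the percentage as "Percentage of subjects in the subgroup with SCC [and other neoplasia". An event count E is the only other column. There is no overall row.

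**Method for the endpoints.** Protocol 10.10.6.1 has the 3-year cumulative incidence in each treatment group estimated "using methods of survival analysis for estimation of cumulative incidence in the presence of censored time-to-event data". SAP 7.3.1 sets the censoring rules: Table 1 for the safety set, Table 2 for the per-protocol (PP) set. SAP 7.5.3 refers drop-outs and missing biopsy results to those rules. SAP 7.3.2 specifies 1 minus Kaplan-Meier.

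**Other SCC incidence shells.** Shells 5, 6 and 9 give cumulative incidence with intervals. Shell 6 adds subject-years. Shell 7 gives events per 100 patient-years.

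**Subgroup summaries.** SAP 7.5.1 states: "Summaries by subgroup will include presentation of the endpoint in question by subgroup and overall".

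**PP set.** SAP 7.5.6 says "the subject will be in the PP analysis set until the day when the deviation takes place". SAP 6 names both censoring and full exclusion, and links staying in until censoring to time-to-event analyses.

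**The concern.** SCC can be found only while a subject is still being examined. Someone who leaves at Month 6 contributes half a year of observation, but in Shell 8 counts in N exactly like someone examined to Month 36. The percentage therefore mixes the risk of SCC with the completeness of follow-up.

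What is at stake is comparability. Country, anatomical location and SCC history are the randomisation strata, and Shell 8 is where the listed tables set out SCC incidence by all three. The trial is open label and lasts 36 months, and withdrawn subjects are not replaced, so equal follow-up across subgroups or arms cannot be taken for granted. If it is unequal, two groups with the same risk will show different percentages, and nothing in the table would reveal this.

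**Working it through.** **1. The plan's own figures.** Protocol 10.3 gives average upper 95% limits of 2.26% and 4.48% for true 3-year rates of 1.0% and 2.5% with 240 per arm. The Wald limit p + 1.96 × √(p(1−p)/240) gives 2.259% and 4.475%, so both reproduce. The calculation uses all 240 subjects and contains no drop-out rate, and none appears elsewhere. The drop-out values below are assumptions.

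**2. Direction.** A Kaplan-Meier event adds S(t−)/(number still at risk), which is at least 1/N and exceeds 1/N once anyone has been censored. So n/N cannot exceed 1 minus Kaplan-Meier on the same subjects and period. In simulation (four scenarios, 4,000 trials each) it never did. With 240 subjects, a true rate of 2.5% and 20% drop-out, the mean n/N was 2.24% and the mean Kaplan-Meier estimate 2.50%.

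**3. Size under steady drop-out.** Assume a constant SCC hazard h = −ln(1−p)/3 and an independent drop-out hazard c = −ln(1−d)/3. Then

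expected n/N = h/(h+c) × [1 − exp(−3(h+c))].

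For p = 2.5% and d = 20%: 3h = 0.02532 and 3c = 0.22314, so h/(h+c) = 0.1019. The bracket is 1 − 0.975 × 0.80 = 0.22. The product is 2.24%.

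| Drop-out by Month 36 | Expected n/N (true 2.5%) | Gap, points | Relative |
|---|---|---|---|
| 10% | 2.37% | 0.13 | 5% |
| 20% | 2.24% | 0.26 | 10% |
| 30% | 2.10% | 0.40 | 16% |

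The relative figures are the same to the nearest percent at a true rate of 1.0%. If all drop-out fell at Week 20, they would be 9%, 17% and 26%.

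**4. Unequal follow-up.** Two subgroups with the same true 2.5% risk but 5% and 30% drop-out would show 2.44% and 2.10%, a spurious ratio of 0.86.

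**5. Against sampling error.** Take an illustrative subgroup of 80 per arm (240/3). One event is 1/80 = 1.25 points, and the standard error at 2.5% is √(0.025 × 0.975/80) = 1.75 points. The 0.26-point gap at 20% drop-out is 0.0026 × 80 = 0.2 of an event. A whole arm would expect only 2.4 to 6 events (240 × 1.0% to 240 × 2.5%).

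**6. PP tables.** Suppose subjects with a deviation stay in N, their later SCCs are not counted, and 15% drop-out is joined by a further 20%, 30% or 40% PP censoring (all assumed). With c the sum of the two hazards, the same formula gives 2.08%, 1.95% and 1.82%, which is 17%, 22% and 27% below 2.5%. For the first: 3c = −ln(0.85 × 0.80) = 0.3857; 0.02532/0.41098 × (1 − 0.975 × 0.68) = 2.08%. If such subjects are fully excluded, N is close to completers and most of the gap disappears.

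**The case against.** The case for leaving Shell 8 alone has weight. It is a descriptive count table with an openly defined percentage, no test and no interval. Protocol 10.10.6.1 requires survival methods for each treatment group, not for subgroups, so the shell does not breach the protocol. Cells will often hold zero to three events, and the gap is lost in that noise. Kaplan-Meier is not a clean benchmark either: SAP Table 1 censors deaths, so 1 minus Kaplan-Meier runs high where subjects die, whereas n/N rightly treats someone who died without SCC as never developing it. The Month 36 window of ±28 days may also let n include an event after the 36.0-month Kaplan-Meier time point, a minor offset. All of this stands.

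A reader might go further and infer that the subgroup figures cannot be tied to the overall result. The documents do not support that. Shell 5 prints a crude N (%) and E for each arm beside the Kaplan-Meier figure, so crude can be compared with crude. Nor is Shell 8 the only breakdown by a stratification factor: SAP 7.3.2 also summarises biopsy results by country and puts all three factors in the STRATA statement, although no listed table shows curves by stratum.

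A reader might also take the larger PP figures as settled. They rest on SAP 7.5.6 alone. SAP 6 allows full exclusion, and details are left to an analysis set document that is not available here.

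What the objection does not answer is that the SAP treats these endpoints as censored, no text labels the Shell 8 percentage as unadjusted, and the overall presentation called for in SAP 7.5.1 is missing from the shell. Shell 5 shows the crude-to-Kaplan-Meier gap only for a whole arm, so it cannot show whether follow-up differs between subgroups.

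**Conclusion.** The point holds as a low-cost improvement to descriptive tables. The crude percentage sits at or below the Kaplan-Meier figure, and the practical harm is distortion of comparisons when follow-up differs between subgroups or arms. Under 10% to 30% steady drop-out with constant, independent hazards, the understatement is about 5% to 16% relative, or 0.13 to 0.40 points at a true 2.5% rate. These sizes depend on assumed drop-out, and deaths account for part of any gap actually seen. In the PP tables the effect is larger or much smaller according to which reading of SAP 6 and 7.5.6 applies.

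It would be tempting to conclude that the trial understates SCC risk. It does not follow: the primary and secondary incidence estimates use Kaplan-Meier and are unaffected.

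**What to change.** In Shell 8:

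- Keep N, n, % and E, and label the percentage as crude and not adjusted for censoring.
- Add, by subgroup and arm, subject-years at risk to first event or censoring (SAP Table 1, or Table 2 for PP) and first events per 100 subject-years with an exact Poisson 95% CI.
- Add the overall row that SAP 7.5.1 calls for.
- For Tables 2-14 and 2-16, state that PP censoring is the same as in Tables 2-4 and 2-6, so that N and the counting of SCCs after a deviation are defined.

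The cost is a shell edit and a little programming on the time-to-event data already needed for Tables 2-3 to 2-6, with a rate calculation close to Shell 7's. The downside is visibly wide intervals in small subgroups. For example, 2 first events in 80 × 3 = 240 subject-years is 0.83 per 100. The exact Poisson limits for a count of 2 are χ²(0.025; 4 df)/2 = 0.242 and χ²(0.975; 6 df)/2 = 7.22, giving 0.10 to 3.01 per 100 subject-years. That width is a fair picture of what such a subgroup can show.
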